10.3 Required Reporting: FDA, IRB, and MCC's SAE Coordinator

Agency	Criteria for reporting	Timeframe	Form to Use	Submission address/ fax numbers	Copy AE to:
U of MN IRB	Unanticipated death of a locally enrolled subject(s); New or increased risk; Any adverse event that require a change to the protocol or consent form – refer to the IRB website for complete details	Within 5 business days of event discovery	Report Form	[contact]	SAE Coordinator [contact] and copy to Incyte Corporation
	Clinical deviations per current IRB reporting requirements		OnCore Deviation Form		
FDA	Unexpected fatal or life threatening adverse reaction except those that can clearly be determined to be unrelated to INCB7839	7 Calendar-Day	MCC SAE	Submit to CDER as an amendment to IND	SAE Coordinator [contact] and copy to Incyte Corporation
	1) Serious and unexpected adverse reaction except those that can clearly be determined to be unrelated to INCB7839 or 2) increased occurrence of serious suspected adverse reactions over that listed in the protocol or investigator brochure or 3) findings from other sources (other studies, animal or in vitro testing)	15 Calendar-Day			
	All other events per CRF 312.33	At time of IND annual report	Summary format	Submit as part of the IND annual report	n/a
	Note: Events clearly determined to be unrelated to INCB7839 and felt due to the disease under treatment. the recent transplant or an underlying medical condition will not require expedited reporting to the FDA for the purposes of this study				
Masonic Cancer Center SAE Coordinator	Events that count toward a dose limiting toxicity or stopping rule	At time of reporting	Event Form	SAE Coordinator [contact]	Not applicable

In each IND safety report, the sponsor must identify all IND safety reports previously submitted to the FDA concerning a similar suspected adverse reaction and must analyze the significance of the suspected adverse reaction in light of the previous, similar reports.

The SAE Coordinator will provide the Masonic Cancer Center's Data and Safety Monitoring Council (DSMC) with the SAE in an appropriate format depending on the individual SAE (as reported or in a summary format).

11 Study Data Collection and Monitoring

11.1 Data Management

This study will collect regulatory and clinical data using University of Minnesota CTSI's instance of OnCore® (Online Enterprise Research Management Environment).

The Oncore database resides on dedicated secure and PHI compliant hardware consisting of 3 physical servers: dev, DR, and production. The dev server is located in the University of Minnesota (UMN) datacenter (WBOB) and houses six database instances (test, train, sandbox, mcc reports, oncdm, and vendor) that are backed up locally because the data is refreshed from Oncore production data. The production server is located in the UMN datacenter (WBOB). All the data servers are managed by the Academic Health Center – Information Systems (AHC-IS) virtual servers which utilize clustered infrastructure to provide real-time failover of virtual servers. This real-time clustering is physically limited to the UMN data center. All relevant AHC IS procedures related for PHI compliant servers (as required by the Center of Excellence for HIPAA Data) apply to Oncore databases.

The integrated data will be stored in PHI compliant servers managed by AHC IS with access given to those authorized users in the Clinical and Translation Science Institute Informatics team (CTSI BPIC and MCC CISS). The data will be integrated and extracted to researchers through the CTSI Informatics team and will be delivered through secure and compliant mechanisms (e.g. AHC IE data shelter, BOX, sftp, etc). If data de-identification is needed, then compliant AHC IE data de-identification tools will be used. The informatics team will grant the IRB approved study team members access to data.

Additional data about correlative laboratory samples generated by the Masonic Cancer Center Translational Therapy Laboratory (TTL) from the protocol-directed correlative research samples is stored in their Laboratory Information Management System (LIMS). The LIMS database application is also stored on a production server located in the UMN datacenter (WBOB) and is managed by the Academic Health Center

Key study personnel are trained on the use of OnCore and will comply with protocol specific instructions embedded within the OnCore.

11.2 Case Report Forms

Participant data will be collected using protocol specific electronic case report forms (e-CRF) developed within OnCore based on its library of standardized forms. The e-CRF will be approved by the study's Principal Investigator and the Biostatistician prior to release for use. The Primary Clinical Research Coordinator or designee will be responsible for registering the patient into OnCore at time of study entry, completing e-CRF based on the patient specific calendar, and updating the patient record until patient death or end of required study participation.

11.3 Data and Safety Monitoring Plan (DSMP)

The study's Data and Safety Monitoring Plan will be in compliance with the University of Minnesota Masonic Cancer Center's Data & Safety Monitoring Plan (DSMP), which can be accessed at <http://z.umn.edu/dmsp>.

For the purposes of data and safety monitoring, this study is classified as high risk (under a locally held IND). Therefore the following requirements will be fulfilled:

- The PI will complete and submit a quarterly Trial Progress Report to the Masonic Cancer Center Data and Safety Monitoring Council (DSMC) with the understanding the Cancer Protocol Review Committee (CPRC) may require more frequent reporting.
- The PI will comply with at least twice yearly monitoring of the project by the Masonic Cancer Center monitoring services.
- The PI will oversee the submission of all reportable adverse events per the definition of reportable in section 10.3 to the Masonic Cancer Center's SAE Coordinator, the University of Minnesota IRB, and the FDA.

11.4 IND Annual Reports

In accordance with regulation 21 CFR § 312.33, the sponsor-investigator with assistance from the MCC Clinical Trials Office (CTO) will submit a progress report annually. The report will be submitted within 60 days of the anniversary date that the IND went into effect.

11.5 Monitoring

The investigator will permit study-related monitoring, audits, and inspections by the Masonic Cancer Center or their designee, IRB, government regulatory bodies, and University of Minnesota compliance groups. The investigator will make available all study related documents (e.g. source documents, regulatory documents, data collection instruments,

study data, etc.). The investigator will ensure the capability for inspections of applicable study-related facilities (e.g. pharmacy, diagnostic laboratory, etc.) will be available for trial related monitoring, audits, or regulatory inspections.

11.6 Record Retention

The investigator will retain study records including source data, copies of case report form, consent forms, HIPAA authorizations, and all study correspondence in a secured facility for at 6 years after the study file is closed with the IRB and FDA.

In addition, the Clinical Trials Office (CTO) will keep a master log of all patients participating in the study with sufficient information to allow retrieval of the medical records for that patient.

Please contact the CTO before destroying any study related records.

12 Correlative Endpoints

To compared expression of CD16 and CD62L on natural killer (NK) cells and ADCC and IFN gamma production prior and after treatment with rituximab and after rituximab + INCB7839 (each patients is his/her own control). We will also determine the soluble CD16 and CD62L levels in vivo and soluble level of stress ligands MICa, MICb, UPBP3 before and after INCB7839 therapy.

13 Statistical Considerations

13.1 Rationale

We recently analyzed outcomes of 80 patients with diffuse large B cell lymphoma (DLBCL) who received autologous hematopoietic stem cell transplant at University of Minnesota between 1984 and 2002 (5). The median age was 47 years and most patients were in complete or partial remission. Post-transplant, the progression free survival at 5 years was 32% (95%CI 22-42%). We identified high risk group (high risk features defined by IPI score) and low risk group with widely different median PFS of 2 months (high risk group) versus 8 months (low risk). Based on Kaplan – Meyer PFS curve, we expect 65% of patients to be progression-free at 6 months.³

Recent prospective multicenter study comparing two different conditioning regimen prior to autograft for DLBCL demonstrated similar 6 months progression free survival of 65-70%.^{1,2} The most common cause of treatment failure is lymphoma progression/relapse.

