The primary goal of the dose finding phase is to determine the maximum tolerated dose (MTD) of INCB7839. Up to three dose levels of INCB7839 will be tested (100 mg bid, 200 mg bid, and 300 mg bid). As the 300 mg bid has been proven safe in the non-transplant setting, dose escalation will follow a Fast-Track Design with 1 patient enrolled per dose level until a grade 2 or greater treatment emergent adverse event occurs. A treatment emergent adverse event is any event not present prior to the initiation of the treatment (INCB7839) or any event already present that worsens in either intensity or frequency following exposure to the treatment. At that point, dose escalation will convert to a standard 3+3 design with two additional patients enrolled at the same dose level. If dose level 3 is completed without dose limiting toxicity (DLT) in the 1st 3 patients, an additional 3 patients will be enrolled at this level (without the staggering required by the DLT rules) prior to moving to the phase II component. DLT is defined in section 7.2.2 of the protocol.

Once the phase I dose escalation is completed, an additional 12 patients will be enrolled at the MTD (or dose level 300mg bid, if no DLT) to obtain a more detailed toxicity profile as well as a preliminary estimate of progression free survival at 6 months post-transplant. Persons receiving less than 10 weeks of INCB7839 and/or fewer than 2 doses of rituximab will be replaced for the primary endpoint analysis.

Patients will be followed for 1 year from transplant for progression free survival (PFS) and overall survival (OS).

5 Patient Selection

Study entry is open to patients 18 years and older regardless of gender or ethnic background. While there will be every effort to seek out and include women and minority patients, the patient population is expected to be similar to that of autologous HCT studies at the University Of Minnesota since this is a requirement for study entry.

Inclusion Criteria

- 5.1 Patients 18 years or older who have undergone an autologous HCT for the treatment of DLBCL and are in a complete remission (CR), partial remission (PR) or have stable disease (SD) at the day 28 post-transplant reassessment
- 5.2 Karnofsky Score of $\geq 70\%$ (appendix II)
- 5.3 Able to start the protocol therapy (1st dose of rituximab) between day 28-75 post-transplant
- 5.4 Adequate organ function defined as:

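### The 65% null for 6-month PFS carries no stated day-28 selection, but trial patients must reach day 28 in CR, PR or SD, may start up to day 75, and are counted from transplant

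*Combined protocol and SAP*

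**What the plan says.** Section 13.1 draws its reference rate from "80 patients with diffuse large B cell lymphoma (DLBCL) who received autologous hematopoietic stem cell transplant" between 1984 and 2002. From that series' Kaplan-Meier curve it concludes that "we expect 65% of patients to be progression-free at 6 months". It adds that "most patients were in complete or partial remission" but gives no time for that assessment. The same paragraph reports 5-year PFS of 32% and median PFS of 2 months (high risk) and 8 months (low risk). A second, multicentre source is quoted at 65-70%. Neither source is described as limited to patients who were progression-free at day 28.

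Section 13.3 makes 65% the null against 85%, with 18 patients, two-sided 0.05 and 79% power. It does not name the test.

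Criterion 5.1 requires complete remission, "partial remission (PR) or have stable disease (SD) at the day 28 post-transplant reassessment". Criterion 5.3 and section 6 allow the first rituximab dose up to day 75. Section 7.1 still says day 60, and these passages must be reconciled. The primary objective (1.1) is PFS at 6 months after transplant, and section 4 counts follow-up from transplant.

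Section 13.4 plans Kaplan-Meier estimation of PFS. Sections 13.1 to 13.4 contain no landmark, delayed-entry adjustment or matched control.

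**The concern.** Every trial patient is known to be free of progression at the day-28 reassessment, yet the clock has been running since transplant. At least 28 of roughly 183 days are therefore event-free by design. The reference patients, as described, were at risk throughout. Section 2.1 says relapse is especially frequent in the first 6 months after transplant, so early failures should not be assumed negligible.

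The trial has no control arm, and 65% is the only efficacy yardstick it states. If part of the distance between the observed rate and 65% comes from who could enter, a reader will credit that part to INCB7839.

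**Working it through.** **Inputs.** Null 65%, alternative 85%, N = 18, accrual 18 months, follow-up 6 months, implied medians 9.7 and 25.5 months (13.3). Reference medians 2 and 8 months and 5-year PFS 32% (13.1). Entry day 28 to 75 (5.1, 5.3). With 30.44 days per month, day 28 is 0.920 months and day 75 is 2.464 months. S(day 28) in the reference series is not given.

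**The plan's own figures.** Constant hazard gives medians of 6·ln 2/(−ln 0.65) = 9.65 months and 6·ln 2/(−ln 0.85) = 25.6 months, so 13.3 assumes constant hazard. For a one-sample log-rank test (inferred), power = Φ{[(E − O) − 1.96√E]/√O}. Here O is the number of events expected under the alternative and E the number expected for the same follow-up at the null hazard. With E = 15.61 and O = 5.89, power is 0.793 (0.751 by simulation). A cube-root exponential test gives about 0.80. The stated 79% is sound for a 65% null.

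**No-effect rate given entry.** A patient known to be progression-free at time t has 6-month PFS of S(6 months)/S(t).

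- Entry at day 28, constant hazard: S(28) = 0.65^(0.920/6) = 0.936, and 0.65/0.936 = 69.4%.
- Entry at day 75, constant hazard: 0.65^(1 − 2.464/6) = 77.6%.
- Starts spread evenly over days 28 to 75, with each patient progression-free until the start (both assumptions): the average of S(6)/S(t) is 73.4%.
- Other values of S(28): 0.95 gives 0.65/0.95 = 68%, 0.90 gives 72%, and 0.85 gives 76%.

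The excess over 65% is 4.4 points for day-28 entry and 8.4 points for the even spread.

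**Chance that an inactive drug passes a test against 65%.** The nominal upper tail is 2.5%.

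| Test | No selection | Entry at day 28 |
|---|---|---|
| One-sample log-rank, simulated | 1.5% | 3.0% |
| One-sample log-rank, asymptotic | 2.5% | 4.4% |
| Cube-root exponential, simulated | 2.4% | 4.8% |
| Exact binomial, at least 16 of 18 | 2.4% | 5.4% |

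The asymptotic row uses E = O = 11.43 without selection. With the hazard starting at day 28 and E counted from transplant, E = 12.17 and O = 10.98.

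**Power at N = 18 against 69.4%** (log-rank formula, hazard from day 28). It depends on the alternative:

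- Same hazard ratio, ln 0.85/ln 0.65 = 0.377 (87.1% at 6 months): 76%.
- Same 20-point gain (89.4%): 92%.
- Alternative kept at 85%: 58%.

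**Is 65% itself consistent with 13.1?** Under constant hazard, the 8- and 2-month medians give 6-month PFS of 0.5^(6/8) = 59% and 0.5^(6/2) = 12.5%. Given day 28 they become 0.5^(5.08/8) = 64% and 0.5^(5.08/2) = 17%. For day-28 entry, 65% would be the matched rate if the unselected rate were 0.65^(1/(1 − 0.920/6)) = 60%.

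Constant hazard is itself a poor description: it implies 5-year PFS of 0.65^10 = 1%, against the stated 32%. A Weibull curve through 65% at 6 months and 32% at 5 years (shape 0.422) has S(28) = 0.823 and a matched rate of 0.65/0.823 = 79%. With the same shape, the 8- and 2-month medians give 71% and 55% given day 28.

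**The case against.** The strongest reply is that no net bias has been shown. S(day 28) is missing, the source curve cannot be read from the document, and plausible conditional rates fall on both sides of 65%. This stands, and it rules out the tempting inference that 65% is simply too low and the trial is tilted towards success. What the documents do support is narrower: selection on reaching entry progression-free can only raise the matched rate.

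A second reply is that 69% lies inside the 65-70% quoted from the multicentre study. That is true of the number, but the second source is not described as day-28 selected either. The same division would apply to it.

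A third is that phase II seeks a preliminary estimate and 18 patients give little precision: an observed 12 of 18 has an exact 95% interval of 41% to 87%. This limits the consequence. A reader might infer from 13.3 that the trial will wrongly declare success, or that its error rate doubles to an unacceptable level. Section 13.4 contains no success rule, and the simulated log-rank error only moves from conservative to about nominal. The other tests do exceed 2.5%, but the protocol names none of them.

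A fourth is that a day-28 landmark would not match the analysed patients anyway. This is correct on two counts. Starts may be as late as day 75. Section 4 also replaces, for the primary analysis, patients with under 10 weeks of INCB7839; section 7.3 limits this to reasons other than toxicity. Progression ends treatment under 7.3, so replacement can remove early progressors. The fix has to cover both.

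**Conclusion.** The mismatch holds: the benchmark has no stated selection, whereas the trial patients are selected at day 28 or later and credited with the time before entry. Taken alone, this makes 65% too low a no-effect rate by an amount the documents do not fix. Under the constant hazard of 13.3 it is about 4 points for entry at day 28 and about 8 points for an even spread of starts over days 28 to 75. The even spread, and freedom from progression until a late start, are assumptions. For entry at day 28, the upper-tail error against 65% moves from about 1.5-2.5% to about 3-5%, depending on the test.

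The overall direction of error in 65% remains open until the figure is reconciled with the 2- and 8-month medians. Nor does a single power loss follow, since power depends on which alternative is kept. The harm is a possibly misleading comparison. It is worth correcting because it is the trial's only efficacy context.

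**What to change.** - **13.1:** Derive the benchmark from the reference curve as S(6 months)/S(t), at day 28 and averaged over the trial's actual entry days. Reconcile it with the stated medians. Fix it from the reference data before phase II PFS is tabulated.
- **13.4:** Estimate PFS with delayed entry at each patient's actual start (equivalently, from the day-28 landmark with late starters joining the risk set at their start day), with a 95% CI. Compare this with the day-28 ratio, which is what it estimates. If an ordinary curve from transplant is also shown, compare that with the entry-averaged rate. Print the original 65% beside both.
- **13.4:** Add a sensitivity estimate that keeps every treated patient, because neither a landmark nor delayed entry corrects for replacement.
- **13.3:** Name the test and restate power at N = 18 against the conditional rate, saying whether the alternative keeps the hazard ratio, the 20-point gain or 85%.

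The cost is one re-analysis or curve reading plus wording. Enrolment, visits and treatment do not change. The documents do not say whether patient-level reference data are available. The benchmark would be added after phase II opened in April 2016, so it must be documented as such and must not silently replace 65%. The apparent effect may also be smaller.

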2.1 Enhancing Cure Rate Of DLBCL After Autologous Hematopoietic Cell Transplant

Non-Hodgkin lymphoma (NHL) is the second most common hematologic malignancy. Diffuse large B cell lymphoma (DLBCL), the most common lymphoma subtype (30-40%), is an aggressive cancer that is rapidly fatal unless promptly treated. In the US, approximately 440,000 patients were treated for NHL in 2010 (SEER.gov). Patients with DLBCL experience frequent relapse and estimated 5-year survival rate is less than 50%.^{1, 2}

Standard treatment includes the use of high-dose chemotherapy with autologous hematopoietic cell transplantation for patients with

chemosensitive recurrence. Although most patients initially achieve a remission, treatment fails for most patients. The relapse incidence is particularly high during the first 6 months after transplant³ (**Figure 1**). There is an urgent need to develop well-tolerated and effective therapies to sustain remission in DLBCL. In this proposal, we hypothesize that chemoresistant

[figure not shown]

Figure 1. Progression free survival in DLBCL after autologous transplant in low and high risk groups defined by International Prognostic Index at relapse¹

lymphoma cells surviving post autologous transplantation retain sensitivity to cellular immune-mediated killing. This hypothesis is supported by clinical evidence that human natural killer (NK) and T cells can be used to treat cancer.^{4,5} NK cells (defined as CD3⁻CD56⁺) are capable of killing virally infected or transformed cells without prior sensitization; however, autologous

NK cells have to be activated to kill. Proposed trial presents the novel approach of combining monoclonal antibody therapy with the newly

discovered strategy of augmenting both NK cell function and tumor homing. The treatment goal is to eliminate chemoresistant lymphoma cells after autologous transplantation.

[figure not shown]

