13.3 Phase II Power Calculation

If all three dose levels are tested, 3-18 patients will be enrolled in the first phase of the trial in order to establish the MTD. Additional 12 patients will be enrolled in the phase II component to obtain 18 patients treated at MTD. Therefore a maximum total of 15 to 30 patients will be involved in the study. In Phase II the designed sample size of 18 for 6 month progression free survival comparison will have a power of 79% to detect the difference between the null hypothesis 6 month progression free survival rate of 65% and the alternative hypothesis of progression free survival of 85% (this is equivalent test the null hypothesis of median disease survival time of 9.7 months and the alternative hypothesis median disease survival time of 25.5 months) at a 0.05 significance using two-sided test. The accrual time will be 18 months and follow up time is 6 months.

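### Section 13.3's 9.7-month null median does not fit the cohort behind the 65% figure, and the stated 79% power was recovered only under the exponential model that produces it

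*Combined protocol and SAP*

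**What the plan says.** Section 13.1 reports "outcomes of 80 patients with diffuse large B cell lymphoma" transplanted at the institution, with 5-year PFS of 32% (95% CI 22-42%). It splits them by International Prognostic Index (IPI) into two groups with "widely different median PFS of 2 months (high risk group) versus 8 months (low risk". From the cohort's Kaplan-Meier curve it concludes that "we expect 65% of patients to be progression-free at 6 months", and it adds a multicenter study with 6-month PFS of 65-70%. The caption of Figure 1 in Section 2.1 names the same two groups and no third: "Progression free survival in DLBCL after autologous transplant in low and high risk groups".

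Section 13.3 sets "the null hypothesis 6 month progression free survival rate of 65" per cent against an alternative of 85%. It describes this as equivalent to testing a "null hypothesis of median disease survival time of 9.7 months" against one of 25.5 months. With 18 patients, two-sided 0.05, 18 months of accrual and 6 months of follow-up, it states 79% power.

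**The concern.** The 65% reference is the only benchmark for efficacy in an uncontrolled study of 18 patients. Section 13.3 attaches a median to it, and that median lies above the medians of both risk groups in the cohort that Section 13.1 offers as its source. A pooled median cannot exceed both group medians. If the power figure was computed through this conversion, it rests on a survival model that the plan's own data contradict. It may also not describe the comparison of 6-month PFS that the section names.

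**Working it through.** **Inputs.** From 13.1: group medians 2 and 8 months, 65% at 6 months, 32% at 5 years. From 13.3: null 65% (9.7 months), alternative 85% (25.5 months), n = 18, two-sided 0.05, accrual 18 months, follow-up 6 months.

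**1. Reproduce the medians.** With a constant hazard, median = 6 × ln 2 / (−ln S(6)).
- Null: 4.159 / 0.4308 = 9.65 months.
- Alternative: 4.159 / 0.1625 = 25.6 months.

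These match 9.7 and, to rounding, 25.5. The equivalence is therefore an exponential conversion.

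**2. Bound the cohort median.** Let w be the high-risk share. Then S(8) = w × S_high(8) + (1 − w) × S_low(8). The low-risk term is 0.50 at its median. The high-risk term is at most 0.50, because that group's median has passed. So S(8) ≤ 0.50 for every w, and the pooled median is at most 8 months. The exponential null instead gives S(8) = 0.65^(8/6) = 56.3%.

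**3. Check the 5-year figure.** The same model gives S(60) = 0.65^10 = 1.3% (1.4% if the rounded 9.7 months is used). Section 13.1 quotes 32%, with a lower confidence limit of 22%.

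**4. Reproduce the power.** The hazards are 0.0718 per month (null) and 0.0271 per month (alternative).
- Events expected under the alternative with uniform accrual: 18 × [1 − (0.85 − 0.85^4) / (18 × 0.0271)] = 5.89.
- Events that the null hazard predicts over the same exposure: 5.89 × 0.0718 / 0.0271 = 15.6.
- One-sample log-rank power: Φ[(15.6 − 5.89 − 1.96 × √15.6) / √5.89] = 79.3%.

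This matches the stated 79%. The plan does not name the method, so the match is an inference. Other two-sided methods tried did not return 79%:
- a simpler one-sample log-rank formula, 69.2% (79.3% only if one-sided);
- tests of the log hazard, 65.8% or 83.1% depending on the variance used;
- normal approximations for a proportion, 40-66%;
- complementary log-log at 6 months, 36-62%.

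**5. Power for a comparison at 6 months.** Exact binomial, n = 18, rejecting for 16 or more progression-free:
- Tail probability at 65%: 0.0004 + 0.0042 + 0.0190 = 0.024.
- Power at 85%: 0.0536 + 0.1704 + 0.2556 = 48.0%.

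Lowering the cut-off to 15 would raise the tail probability at 65% to about 0.078, above 0.05.

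**The case against.** **A reader might infer that 65% itself is contradicted.** With 65% at 6 months and at most 50% at 8 months, the hazard must rise from 0.072 to at least ln(0.65/0.50)/2 = 0.131 per month, about 1.8-fold. Section 2.1 says: "The relapse incidence is particularly high during the first 6 months after transplant". The documents do not support this stronger reading, for five reasons.
- Medians do not fix the 6-month value. For illustration, 20% high-risk at 25% and 80% low-risk at 75% give 0.05 + 0.60 = 65%, and both medians remain possible.
- Section 2.1 does not compare months 0-6 with months 6-8. In 80 patients, ignoring censoring, the 1.8 ratio would rest on about 28 and 12 events. Its approximate 95% interval is 0.93-3.6, so a flat hazard is not excluded.
- The multicenter study gives 65-70% independently of the cohort.
- Patients enter in response or with stable disease and start between day 28 and day 75, which removes early failures. With an 8-month exponential median, 6-month PFS given freedom from progression is 0.5^(5.08/8) = 64.4% from day 28 and 0.5^(3.54/8) = 73.6% from day 75. The plan does not say it made this adjustment, but the adjustment favours 65%.
- Figure 1 could not be seen and may already show the group curves.

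**A reader might also infer that risk mix could pass for the drug effect.** Under exponential groups, 6-month PFS is 59.5% (low risk) and 12.5% (high risk), so a 10-point change in high-risk share moves the result by 4.7 points. Matching the hypothesised 20 points would take a shift of about 43 points (20 / 0.47). It also cannot be said that IPI goes uncollected. It is not listed in Section 8.1, but medical history is taken, the case report forms are not reproduced, and a transplant database is used.

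**Two further points for the plan stand.** Section 13.3 offers 9.7 months as a conversion of 65%, not as an observed cohort median. And the aim is a preliminary estimate: Section 13.4 plans Kaplan-Meier estimation and specifies no test against 65%. These limit the consequence. They do not rescue the equivalence or the power figure that relies on it.

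**Conclusion.** The equivalence does not hold for the source cohort: 9.7 months against a pooled median of at most 8, and about 1.3% against 32% at 5 years. The median bound assumes only that the two risk groups make up the cohort. If some patients were unclassified, it covers the classified patients only.

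Among the two-sided methods tried, the stated 79% was recovered only under this exponential model. For a comparison of 6-month PFS, the exact binomial figure is about 48%.

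Whether 65% is the right null is left open. If it is too high, it is conservative for false positives, at a cost in power. For illustration, suppose the untreated rate were 59.5% (the 8-month exponential value) and the drug added 20 points. The formula in step 4 against a 65% null would then give 39.6%.

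**What to change.** In Sections 13.1 and 13.3, reconcile the figures in one of two ways:
- state the cohort's pooled 6-month Kaplan-Meier PFS and median, with the group sizes and preferably conditional on being progression-free at entry, and use that figure; or
- rest 65% on the multicenter study alone.

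In either case, drop the 9.7/25.5-month equivalence, name the test or estimate intended at 6 months, and restate the power for it.

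Abstract IPI at relapse from the existing transplant records, if it is not already captured, and report the enrolled risk mix beside the 6-month PFS estimate.

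The cost is protocol wording, possibly one baseline field, and one line in the results. The downside is that the stated power becomes less favourable.
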